5.8 Randomization/Drug Assignment

Not applicable.

5.9 Protocol Deviations

AbbVie does not allow intentional/prospective deviations from the protocol except when necessary to eliminate an immediate hazard to study participants. The investigator is responsible for complying with all protocol requirements, written instructions, and applicable laws regarding protocol deviations. If a protocol deviation occurs (or is identified), the investigator is responsible for notifying IEC/IRB, regulatory authorities (as applicable), and AbbVie.

5.10 Data Monitoring Committees

An external DMC composed of clinicians and a statistician independent of AbbVie and with relevant expertise in their field will review data from the ongoing study. The DMC is responsible for safeguarding the interests of trial participants, assessing the safety of the interventions during the trial, as well as for monitoring the integrity and interpretability of the trial. The DMC will provide recommendations to the sponsor regarding ongoing trial conduct or modifications to the trial as described in a separate DMC charter.

An external statistical data analysis center (SDAC) is responsible for performing the analyses described in the DMC charter as well as additional analyses requested by the DMC and facilitating interpretation and answering questions that arise before, during or after DMC review.

The DMC will regularly review safety data from the ongoing study according to the schedule provided in the DMC charter, including included as appropriate AEs, laboratory values, vital sign values and ECG results.

A separate DMC charter will be prepared outside of the protocol and will further describe the roles and responsibilities of the DMC members, frequency and scope of the data reviews, and expectations for communications.

The atogepant HEAC will monitor events of post-treatment elevations of ALT and/or AST $\geq 3 \times$ ULN to determine whether the elevation was related to atogepant.

6 SAFETY CONSIDERATIONS

6.1 Complaints and Adverse Events

Complaints

A complaint is any written, electronic, or oral communication that alleges deficiencies related to the physical characteristics, identity, quality, purity, potency, durability, reliability, safety, effectiveness, or performance of a product/device. Complaints associated with any component of this investigational product must be reported to AbbVie.

Product Complaint

A product complaint is any complaint related to the biologic or drug component of the product or to the medical device component(s).

For a product this may include, but is not limited to, damaged/broken product or packaging, product appearance whose color/markings do not match the labeling, labeling discrepancies/inadequacies in the labeling/instructions (e.g., printing illegible), missing components/product, device damage or not working properly, or packaging issues.

Product complaints concerning the investigational product and/or device must be reported to AbbVie within 24 hours of the study site's knowledge of the event.

Reporting will be done via electronic data capture (EDC). The date the product complaint details are entered into EDC and the form is saved represents the date reported to AbbVie. A back-up paper form will be provided for reporting complaints related to unassigned product or in the event of an EDC system issue. If a back-up paper form is used, the date the form is emailed to [contact] represents the date reported to AbbVie.

All follow-up information is to be reported to the sponsor (or an authorized representative) and documented in source as required by the sponsor. Product complaints associated with AEs will be reported in the study summary. All other complaints will be monitored on an ongoing basis. Product complaints occurring during the study will be followed up to a satisfactory conclusion.

Medical Complaints/Adverse Events and Serious Adverse Events

An AE is defined as any untoward medical occurrence in a participant or clinical investigation participant administered a pharmaceutical product and which does not necessarily have a causal relationship with this treatment. An AE can therefore be any unfavorable and unintended sign (including an abnormal laboratory finding), symptom, or disease temporally associated with the use of a medicinal (investigational) product, whether or not the event is considered causally related to the use of the product.

Such an event can result from use of the drug as stipulated in the protocol or labeling, as well as from "special situations" such as accidental or intentional overdose, medication error, occupational or accidental exposure, off-label use, drug abuse, drug misuse, or drug withdrawal, all which must be reported whether associated with an AE or not. Any worsening of a pre-existing condition or illness is considered an AE. Worsening in severity of a reported AE should be reported as a new AE. Laboratory abnormalities and changes in vital signs are considered to be AEs only if they result in discontinuation from the study, necessitate therapeutic medical intervention, meets protocol-specific criteria, and/or if the investigator considers them to be AEs.

The investigators will monitor each participant for clinical and laboratory evidence of AEs on a routine basis throughout the study. All AEs will be followed to a satisfactory conclusion.

An elective surgery/procedure scheduled to occur during a study will not be considered an AE if the surgery/procedure is being performed for a pre-existing condition and/or the surgery/procedure has been pre-planned prior to study entry. However, if the pre-existing condition deteriorates unexpectedly during the study (e.g., surgery performed earlier than planned), then the deterioration of the condition for which the elective surgery/procedure is being done will be considered an AE.

If any of the following events are reported, then the following supplemental report must be completed.

Event	Supplemental Report
Cardiac events Arrhythmias Myocardial infarction or unstable angina Heart failure Cerebral vascular accident and transient ischemic attack Cardiovascular procedures (SAE Supplemental Procedure eCRF)	Major adverse cardiovascular events (MACE) eCRF
Discontinuation or interruption of study drug due to a hepatic-related AE A hepatic-related SAE ALT/AST $\geq 3 \times$ ULN or ALT/AST $\geq 3 \times$ ULN with a total bilirubin $\geq 2 \times$ ULN	Hepatic AE eCRF

If an AE, whether associated with study drug or not, meets any of the following criteria, it is to be reported to AbbVie clinical pharmacovigilance as an SAE within 24 hours of the site being made aware of the SAE (refer to Section 4.2 of the Operations Manual for reporting details and contact information):

Death of Participant	An event that results in the death of a participant.
Life-Threatening	An event that, in the opinion of the investigator, would have resulted in immediate fatality if medical intervention had not been taken. This does not include an event that would have been fatal if it had occurred in a more severe form.
Hospitalization or Prolongation of Hospitalization	An event that results in an admission to the hospital for any length of time or prolongs the participant's hospital stay. This does not include an emergency room visit or admission to an outpatient facility.
Congenital Anomaly	An anomaly detected at or after birth, or any anomaly that results in fetal loss.
Persistent or Significant Disability/Incapacity	An event that results in a condition that substantially interferes with the activities of daily living of a study participant. Disability is not intended to include experiences of relatively minor medical significance such as headache, nausea, vomiting, diarrhea, influenza, and accidental trauma (e.g., sprained ankle).

**Important Medical Event
Requiring Medical or Surgical
Intervention to Prevent
Serious Outcome**

An important medical event that may not be immediately life-threatening or result in death or hospitalization, but based on medical judgment may jeopardize the participant and may require medical or surgical intervention to prevent any of the outcomes listed above (i.e., death of participant, life threatening, hospitalization, prolongation of hospitalization, congenital anomaly, or persistent or significant disability/incapacity). Additionally, any elective or spontaneous abortion or stillbirth is considered an important medical event along with any suspected transmission of an infectious agent via a medicinal product if no other serious criterion is applicable. Examples of such events include allergic bronchospasm requiring intensive treatment in an emergency room or at home, blood dyscrasias or convulsions that do not result in inpatient hospitalization, or the development of drug dependency or drug abuse.

All AEs reported from the time of study drug administration until 30 days or 5 half-lives, whichever is longer, after discontinuation of study drug administration will be collected, whether solicited or spontaneously reported by the participant. In addition, study procedure-related serious and nonserious AEs will be collected from the time the participant signs the study-specific informed consent.

Adverse Events of Special Interest

The following AEs of special interest will be monitored during the study:

- Treatment-emergent elevated ALT or AST laboratory value that is $\geq 3 \times \text{ULN}$.
- Potential Hy's law cases: elevated ALT or AST laboratory value that is $\geq 3 \times \text{ULN}$ and an elevated total bilirubin laboratory value that is $\geq 2 \times \text{ULN}$ and, at the same time, an alkaline phosphatase laboratory value that is $< 2 \times \text{ULN}$.

Adverse Event Severity and Relationship to Study Drug

The investigators will rate the severity of each AE as mild, moderate, or severe.

The investigator will use the following definitions to rate the severity of each AE:

Mild	The AE is transient and easily tolerated by the participant.
Moderate	The AE causes the participant discomfort and interrupts the participant's usual activities.
Severe	The AE causes considerable interference with the participant's usual activities and may be incapacitating or life threatening.

The investigator will use the following definitions to assess the relationship of the AE to the use of study drug:

Reasonable Possibility	After consideration of factors including timing of the event, biologic plausibility, clinical judgment, and potential alternative causes, there is sufficient evidence (information) to suggest a causal relationship.
No Reasonable Possibility	After consideration of factors including timing of the event, biologic plausibility, clinical judgment, and potential alternative causes, there is insufficient evidence (information) to suggest a causal relationship.

Pregnancy

While not an AE, pregnancy in a study participant must be reported to AbbVie within 24 hours after the site becomes aware of the pregnancy. Participants who become pregnant during the study must be discontinued (Section 5.5). If a pregnancy occurs in a study participant, information regarding the pregnancy and the outcome will be collected.

In the event of pregnancy occurring in a participant's partner during the study, written informed consent from the partner must be obtained prior to collection of any such information. AbbVie will provide a separate consent form for this purpose. Pregnancy in a participant's partners will be collected from the date of the first dose through 30 days following the last dose of study drug.

The pregnancy outcome of an elective or spontaneous abortion, stillbirth or congenital anomaly is considered an SAE and must be reported to AbbVie within 24 hours after the site becomes aware of the event.

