3 OBJECTIVES AND ENDPOINTS

3.1 Objectives, Hypotheses, and Estimands

To evaluate the safety and tolerability of atogepant when added to BOTOX over 24 weeks in participants with CM.

To prospectively evaluate the responder rates and change from baseline in monthly migraine days when atogepant is added to BOTOX monotherapy in participants with CM.

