 INTERVIEW	
 Review concomitant medications and procedures 	
 Adverse events eDiary return visit
 PRO	
 Review eDiary data and compliance C-SSRS PROMIS v2.0 Cognitive Function Abilities Short-Form 6a MSQ v2.1 PHQ-9 	
 GAD-7 WPAI:MIGRAINE PSSM PGIC Complete headache assessments via eDiary (daily) AIM-D eDiary return
 EXAM	
 ECG Physical examination 	
 Collect vital sign measurements (vital sign measurements: sitting BP and pulse rate, respiratory rate, temperature, weight)
 LAB	
 Urine pregnancy test 	
 CENTRAL LAB	
 Collect clinical laboratory samples Optional biomarker collection for CGRP (saliva and plasma) 	
 Lipid profile, marker of inflammation, adipokine hormones, HbA1c
 TREATMENT	
 Completion of atogepant dosing 	
 Administer BOTOX injection (concomitant medication), \pm 7 days

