4 SAFETY MANUAL

4.1 Methods and Timing of Safety Assessment

All serious and nonserious AEs which could be related to study procedures (e.g., infection at liver biopsy site, done during screening) will be collected from the time the participant signed the study-specific informed consent until study drug administration. From the time of study drug administration until 30 days or 5 half-lives after the last dose of study drug or study treatment, all nonserious and serious adverse event (SAE) will be collected whether solicited or spontaneously reported by the participant. After 30 days or 5 half-lives following the last dose of study drug or completion of study treatment only spontaneously reported SAEs will be collected (nonserious AEs will not be collected).

AE = adverse event; SAE = serious adverse event

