10.2.1 Treatment-Emergent Adverse Events

Treatment-emergent AEs (TEAEs) are defined as any AE with the onset that is after the first dose of study drug. Events when the onset date is the same as the study drug start date are assumed to be treatment-emergent. An AE that occurs more than 30 days after the last dose of open-label study treatment will not be counted as a TEAE. All TEAE will be summarized overall, as well as by primary MedDRA SOC and PT. The SOC will be presented in alphabetical order, and the PTs will be presented in alphabetical order within each SOC.

The number and percentage of participants experiencing TEAEs will be summarized.

An AE will be considered a treatment-emergent serious AE (TESAE) if it is a TEAE that additionally meets any SAE criterion.

TEAEs that started after the date of last dose of study treatment will be considered as newly emergent.

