10.2.2 Adverse Event Overview

An overview of AEs will be presented consisting of the number and percentage of participants experiencing at least one event for each of the following AE categories:

- Any TEAE

- Any TEAE related to study treatment according to the investigator
- Any severe TEAE
- Any TESA
- Any TEAE leading to discontinuation of study treatment
- Any TEAE leading to death
- All deaths

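### The main TEAE tables pool time on atogepant plus BOTOX with up to 30 days after the last atogepant dose, and no on-treatment TEAE summary is planned

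*Protocol*

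**What the plan says.** The first objective in Protocol 3.1 is "To evaluate the safety and tolerability of atogepant when added to BOTOX over 24 weeks in participants with CM". Protocol 3.2 and SAP 3.1 make the safety endpoints primary.

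**Before the first dose.** Protocol 6.1 starts full collection with atogepant: "All AEs reported from the time of study drug administration until 30 days or 5 half-lives, whichever is longer" after discontinuation. For the earlier period it says only that "study procedure-related serious and nonserious AEs will be collected from the time the participant signs the study-specific informed consent". Operations Manual 4.1 agrees: events that could be procedure-related "will be collected from the time the participant signed the study-specific informed consent until study drug administration". The schedule in Protocol Appendix D lists adverse events at Visits 1, 1a and 2, but the text limits what is captured there.

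**After the last dose.** The Visit 8 (Week 24) list in Operations Manual 2.1 has "Completion of atogepant dosing" together with a BOTOX injection, ±7 days. SAP 10.2.1 sets the upper limit of the TEAE window: "An AE that occurs more than 30 days after the last dose of open-label study treatment will not be counted as a TEAE". It also says that "TEAEs that started after the date of last dose of study treatment will be considered as newly emergent", and SAP 10.2.3 gives those events their own table by system organ class and preferred term.

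**The main tables.** SAP 10.2.2: "An overview of AEs will be presented consisting of the number and percentage of participants experiencing at least one event", over seven categories. Neither these nor the main SOC/PT tables in SAP 10.2.3 are limited to time on atogepant. SAP 6.0, by contrast, ends treatment duration at the last atogepant dose and summarizes participant-years of atogepant.

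**The concern.** A reader will take the overview and the SOC/PT tables as the adverse-event profile of the combination. For a completer they also cover a month in which atogepant is no longer taken and, on schedule, BOTOX has just been re-injected. Events from that injection count towards the combination's incidence.

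The counts and the planned exposure summary also cover different time. TEAEs run to last dose plus 30 days, while exposure stops at the last dose. Anyone who divides one by the other gets a rate whose numerator and denominator do not match.

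The safety population has about 75 participants and there is no control arm, so these percentages are the main adverse-event result. They should describe a clearly defined period.

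**Working it through.** **1. The plan's own figures.** Protocol 7.7 and SAP 2.4 state a 95% chance of seeing at least one AE of 4% incidence in 75 participants, and 60 completers at 20% early termination.
- 1 − 0.96^75 = 0.953.
- 75 × 0.80 = 60.

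Both reproduce. They are not in dispute and supply n = 75 and the 20% used below.

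**2. Share of the window after atogepant.** Daily dosing for 24 weeks is 168 days (Protocol Appendix D), and SAP 10.2.1 adds 30.
- 30 / (168 + 30) = 30/198 = 15.2%.
- If reporting in practice stops at the Week 28 visit: 28/196 = 14.3%.

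**3. Effect on incidence, constant hazard.** The documents give no background AE rate, so the 24-week incidence q is an assumption. Pooled incidence = 1 − (1 − q)^(198/168). Post-dose incidence = 1 − (1 − q)^(30/168).

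| On-treatment q | Pooled | Post-dose | Pooled minus post-dose |
|---|---|---|---|
| 4% | 4.7% | 0.7% | 4.0% |
| 10% | 11.7% | 1.9% | 9.8% |
| 20% | 23.1% | 3.9% | 19.2% |
| 50% | 55.8% | 11.6% | 44.2% |

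The last column tests whether the newly emergent table can be subtracted from the pooled one. For a rare preferred term it nearly works. For a common row, such as any TEAE, it understates: 44.2% against a true 50% when the two windows are independent. In general, with T participants in the pooled row and N in the newly emergent row, the on-treatment count lies anywhere from T − N to T. The overview categories (related, severe, serious and so on) have no planned newly emergent counterpart at all.

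**4. Effect on injection-related events.** Let p be an assumed risk per injection, independent between injections. Completers have two injections before the post-dose window and three in total: a = 1 − (1 − p)^2 and b = 1 − (1 − p)^3. Let 20% stop before the third injection, with risk x = p (one injection) or x = a (two). The relative rise is (0.8b + 0.2x) / (0.8a + 0.2x) − 1.

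| p | a | b | Rise, x = p | Rise, x = a |
|---|---|---|---|---|
| 2% | 3.96% | 5.88% | 43% | 39% |
| 5% | 9.75% | 14.26% | 41% | 37% |
| 10% | 19.0% | 27.1% | 38% | 34% |

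The range is 34% to 43%. It treats every third injection and its events as falling after the last atogepant dose.

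**5. Denominators.** If the 15 early terminators average 12 weeks (an assumption), exposure as defined in SAP 6.0 is (60 × 168 + 15 × 84) / 365.25 = 31.0 participant-years. Thirty post-dose days for all 75 would add 75 × 30 / 365.25 = 6.2 participant-years that the TEAE counts cover and the exposure summary does not.

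**The case against.** The strongest reply is that the SAP already identifies post-dose events, labels them and tabulates them by SOC and PT. Collected dates would allow an on-treatment count at any time, so what remains is table layout. Much of that is fair. No data are lost and the 30-day window is not an error. But step 3 shows that the planned outputs do not contain the on-treatment figure, and for a primary objective it should be planned.

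A reader might go further and infer that these two rules are why the trial cannot show what atogepant adds to BOTOX. The documents do not support that.
- The main cause is the design. Protocol 4.2 has no control group and Operations Manual 6.4 describes a single arm.
- The safety objective states no contrast with BOTOX alone. In Protocol 4.2 the comparison with BOTOX monotherapy belongs to efficacy.
- Only AE incidence lacks a pre-dose reference. Laboratory tests, vital signs and ECG are analysed as change from a baseline taken on BOTOX (SAP 10.1, 10.3 to 10.5), C-SSRS has pre-dose assessments, and both AESIs are laboratory-defined (SAP Appendix C).
- Run-in symptoms mentioned late do not become TEAEs by rule. SAP 10.2.1 goes by onset date, so that would need a wrong date.
- Recording all AEs from consent would help only in part. An AE of 4% 24-week incidence would be seen at least once in 75 people with probability 1 − 0.96^(75 × d/168): 40% for d = 28 days, 47% for 35, 78% for 84. The reference would also fall mostly late in a BOTOX cycle.

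A larger inflation of 43% to 49%, which is b/a − 1 in step 4, is also tempting. It needs every participant to receive three injections, against the plan's own 20% early termination.

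**Conclusion.** The concern holds in a limited form. The main TEAE tables mix time on the combination with up to 30 days off atogepant, about 15% of a completer's window, and the on-treatment incidence cannot be read from any planned output. The effect is modest for events with a steady background rate: roughly 12% to 17% relative for 24-week incidences of 50% down to 4%. It could reach 34% to 43% for injection-related events.

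The first range assumes a constant hazard and full follow-up. The second assumes independent risks per injection and a third injection that falls after the last dose. Clustering of events in susceptible people, or Visit 8 injections given early in the ±7-day window, would reduce it. The documents give no AE rates with which to choose within these ranges.

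Non-procedure AEs before Day 1 are not collected, so there is no run-in AE rate on BOTOX. That limit should be reported; it does not invalidate the safety analysis.

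**What to change.** 1. In SAP 10.2.2 and 10.2.3, show three columns: first to last atogepant dose, after last dose, and total. The total keeps the 30-day convention unchanged.
2. For the on-treatment column, add exposure-adjusted rates using the participant-years in SAP 6.0. Those are total exposure, so they suit events per participant-year. A first-event rate would need time censored at the event.
3. State in the report that non-procedure AEs were not collected before Day 1, and that the single-arm design cannot attribute AE incidence to atogepant over BOTOX.

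The cost is output shells and wider tables; the dates are already needed for the newly emergent label. The after-last-dose column must not be presented as a clean BOTOX-alone period. It follows recent atogepant exposure, and early discontinuers reach it at other points of the BOTOX cycle.

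Collecting all AEs from consent is optional and not part of this recommendation. It would need a protocol amendment with ethics approval (Protocol 8.1) and would give only the short, late-cycle reference described above.
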